8.9 Management of Toxicities

All AEs should be graded according to [Section 11.3.1](#) and proper action taken based on the clinical findings and grading.

In the following, when a limit for a laboratory parameter in plasma is indicated and the local practice is to have the test in serum, the equivalent value should be considered, and vice versa.

FP-1305 should be withheld for any of the following adverse event at least possibly related to FP-1305:

- 1) Grade 2 pneumonitis (see [Section 8.9.2.1](#))
- 2) Grade 2 or 3 colitis (see [Section 8.9.2.2](#))
- 3) Grade 2 nephritis (see [Section 8.9.2.3](#))
- 4) Grade 2 liver enzyme elevations (see [Section 8.9.2.4](#))
- 5) Grade 2 or 3 endocrinopathy (see [Section 8.9.2.5](#))
- 6) Grade 2 fibrosis due to liver injury (see [Section 8.9.4](#))
- 7) Any other severe or Grade 3 treatment-related adverse reaction
- 8) Prolonged (> 2 weeks) Grade 2 or intolerable Grade 2 toxicity

FP-1305 must be permanently discontinued for any of the following adverse event at least possibly related to FP-1305:

- 1) Any life-threatening adverse reaction (excluding endocrinopathies controlled with hormone replacement therapy and/or immunosuppressants)
- 2) Grade 3 or 4 infusion reaction (see [Section 8.9.1](#))
- 3) Grade 3 or 4 pneumonitis or Grade 2 recurring pneumonitis (see treatment in [Section 8.9.2.1](#))
- 4) Grade 4 colitis (see [Section 8.9.2.2](#))
- 5) Grade 3 or 4 nephritis (see [Section 8.9.2.3](#))
- 6) Grade 3 or 4 hepatic failure (see [Section 8.9.2.4](#))
- 7) Grade 4 endocrinopathy (see [Section 8.9.2.5](#))
- 8) Grade 3 or 4 fibrosis due to liver injury (see [Section 8.9.4](#))
- 9) Inability to reduce the corticosteroid dose to 10 mg or less of prednisone or equivalent per day within 6 weeks from the initiation of the continuous corticosteroid
- 10) Persistent Grade 2 or 3 adverse reactions (excluding endocrinopathies controlled with hormone replacement therapy and/or immunosuppressants) that do not recover to Grade 0-1 within 6 weeks after the last dosing of FP-1305 and that are considered clinically significant
- 11) Any haematological or non-haematological Grade 3 treatment-related adverse reaction that recurs

8.9.1 Infusion Reactions

In case of an infusion reaction, the following documentation should be recorded

- 1) Pre-infusion assessment (i.e., the drugs administered, doses, number of previous infusions of the agent, and infusion rates)
- 2) Initial symptoms and course of progression

- 3) Time when the infusion was initiated and time when the infusion reaction began
- 4) Intervention, timing, and subject response
- 5) Time of symptom resolution

Infusion reactions are generally not considered to be DLT, but this judgement should be conducted after each case. Severe (Grade 3 or 4) reactions should be reported within 24 hours to the Sponsor.

Grade 1 infusion reaction (Mild reaction; no infusion interruption or intervention necessary)

Monitor the subject closely or treatment according to the local practise. Consider prophylactic medication (e.g., paracetamol a.k.a. acetaminophen and diphenhydramine) for next administration.

Grade 2 infusion reaction (Moderate reaction leading to infusion interruption but responsive to symptomatic treatment): Interrupt the infusion but maintain vascular access with normal saline. Paracetamol (a.k.a. acetaminophen) and diphenhydramine (or other antihistamine according to local practises) usage is recommended or treatment according to the local practise. However, diphenhydramine (50 mg) and ranitidine (50 mg diluted in 5% dextrose to 20 mL) given together for anaphylaxis are superior to diphenhydramine given alone. Vital sign assessment should be periodically repeated until the subject is stable. Once the symptoms are totally resolved, the infusion may be restarted at maximum 50% of the previous infusion rate. If the symptoms do not recur during 30 minutes of infusion of this slower rate, the infusion rate may be increased to the normal rate. If symptoms recur, the infusion must be stopped, and the amount infused should be reported. Prophylactic medication for the next administration is highly recommended and the infusion rate should be adjusted (see [Section 8.2.1](#) and [Section 8.2.2](#)).

Grade 3 or 4 infusion reaction (A prolonged reaction that does not rapidly respond to symptomatic treatment, with possible recurrence of symptoms following initial improvement, hospitalization indicated for the clinical sequelae, or life-threatening requiring pressor or ventilatory support): Interrupt the infusion but maintain a vascular access with normal saline. Epinephrine should be considered depending on the severity of the reaction. Corticosteroids may be given IV or orally; oral administration is sufficient in less severe anaphylactic events. Vital sign assessment should be periodically repeated until the subject is stable. The administration of FP-1305 is permanently discontinued.

8.9.2 Immune Related Adverse Events

The aetiology of symptoms that may suggest an irAEs should always be investigated in order to rule out symptoms due to infection or disease progression. Systemic use of corticosteroids is generally prohibited (see [Section 10.2](#)) because a decrease in immune cells in circulation is observed after initiation of corticosteroid treatment and it may counteract the effect of the IMP. Thus, it needs to be carefully evaluated, if the continuation in the study is beneficial for the subject. In such cases, investigator should consult the Sponsor and Medical Monitor for subject continuation.

8.9.2.1 Immune-Mediated Pneumonitis

Monitor subjects for signs and symptoms of pneumonitis. A CT should be performed to confirm diagnosis. Corticosteroids should be administered at a dose of 1 to 2 mg/kg/day prednisone equivalents for Grade 2 or greater pneumonitis. Upon improvement to Grade 1 or less, initiate corticosteroid taper and continue to taper over at least 1 month. Permanently discontinue FP-1305 for severe (Grade 3) or life-threatening (Grade 4) pneumonitis and withhold FP-1305 until the resolution for moderate (Grade 2) pneumonitis. If Grade 2 pneumonitis recurs FP-1305 must be permanently discontinued.

8.9.2.2 Immune-Mediated Colitis

Monitor subjects for immune-mediated colitis. Subjects with Grade 3 or Grade 4 diarrhoea as well as those with Grade 2 diarrhoea with blood in the stools should be evaluated for the presence of colitis. Diagnosis with endoscopy should be considered. Administer corticosteroids at a dose of 1 to 2 mg/kg/day prednisone equivalents followed by corticosteroid taper for severe (Grade 3) or life-threatening (Grade 4) colitis. Administer corticosteroids at a dose of 0.5 to 1 mg/kg/day prednisone equivalents followed by corticosteroid taper for moderate (Grade 2) colitis of more than 5 days duration; if worsening or no improvement occurs despite initiation of corticosteroids, increase dose to 1 to 2 mg/kg/day prednisone equivalents. Upon improvement to Grade 1 or less, initiate corticosteroid taper and continue to taper over at least 1 month. Withhold FP-1305 for Grade 2 or 3 immune-mediated colitis. Permanently discontinue FP-1305 for Grade 4 colitis or for recurrent colitis upon restarting the drug.

Consider adding an agent or other immunosuppressant agents, such as an anti-TNF antibody therapy, for the management of immune-mediated colitis unresponsive to systemic corticosteroids within 3 to 5 days or recurring after symptom improvement. If other immunosuppressive agents are needed for the management of immune-mediated colitis, FP-1305 should be permanently discontinued.

8.9.2.3 Immune-Mediated Nephritis and/or Renal Dysfunction

Corticosteroids should be used (initial dose of 1 to 2 mg/kg/day prednisone or equivalent) for Grade 2 or greater nephritis (creatinine 2 - 3 x above baseline). Upon improvement to Grade 1 or less, initiate corticosteroid taper and continue to taper over at least 1 month. Withhold FP-1305 for moderate (Grade 2) nephritis, and permanently discontinue FP-1305 for severe (Grade 3) or life-threatening (Grade 4) nephritis.

8.9.2.4 Immune-Mediated Hepatitis and/or Liver Dysfunction

Liver tests should be periodically performed (according to the schedule). If immune-mediated hepatitis is suspected, corticosteroids should be used (initial dose of 1 to 2 mg/kg/day prednisone or equivalent followed by a taper) for Grade 2 or greater transaminase elevations (Grade 2 transferase levels $>3.0 - 5.0 \times$ ULN if baseline value was normal; $>3.0 - 5.0 \times$ baseline if baseline value was abnormal) or bilirubin elevations (Grade 2 $>1.5 - 3.0 \times$ ULN if baseline value was normal; $>1.5 - 3.0 \times$ baseline if baseline value was abnormal).

Upon improvement to Grade 1 or less, initiate corticosteroid taper and continue to taper over at least 1 month. In steroid refractory subjects, the use of mycophenolate mofetil 500-1000mg twice a day may be considered and FP-1305 should be permanently discontinued. A liver biopsy should be considered to confirm the diagnosis.

In case of suspected immune-mediated hepatitis related to FP-1305 withhold FP-1305 for moderate (Grade 2) liver enzyme elevation, and permanently discontinue FP-1305 for severe (Grade 3) or life-threatening (Grade 4) hepatic failure if the increase is not clearly related to cancer progression in the liver.

8.9.2.5 Immune-Mediated Endocrinopathies

Subjects should be monitored for clinical signs and symptoms of endocrinopathies. Subjects may present with fatigue, headache, mental status changes, abdominal pain, unusual bowel habits, and hypotension, or nonspecific symptoms which may resemble other causes such as brain metastasis or

underlying disease. Unless an alternate aetiology has been identified, signs or symptoms of endocrinopathies should be considered immune-related.

Withhold FP-1305 for symptomatic hypothyroidism and initiate thyroid hormone replacement if needed. Withhold FP-1305 for symptomatic hyperthyroidism and initiate antithyroid medication if needed. If an acute inflammation of the thyroid is suspected, corticosteroids (initial dose of 1 to 2 mg/kg/day prednisone equivalents) should be considered. Upon improvement, administration of FP-1305 can be resumed after corticosteroid taper. FP-1305 must be permanently discontinued for life-threatening (Grade 4) hyperthyroidism or hypothyroidism. Monitoring of thyroid function should be continued to ensure appropriate hormone replacement is utilised.

Withhold FP-1305 for symptomatic Grade 2 adrenal insufficiency and initiate physiologic corticosteroid replacement if needed. FP-1305 must be permanently discontinued for severe (Grade 3) or life-threatening (Grade 4) adrenal insufficiency. Monitoring of adrenal function and hormone levels should be continued to ensure that appropriate corticosteroid replacement is utilised.

Withhold FP-1305 for symptomatic Grade 2 or 3 hypophysitis, and initiate hormone replacement as needed. If an acute inflammation of the pituitary gland is suspected, corticosteroids (initial dose of 1 to 2 mg/kg/day prednisone or equivalent) should be considered. Upon improvement, administration of FP-1305 can be resumed after corticosteroid taper. FP-1305 must be permanently discontinued for life-threatening (Grade 4) hypophysitis. Monitoring of pituitary function and hormone levels should be continued to ensure appropriate hormone replacement is utilised.

Withhold FP-1305 for symptomatic diabetes, and initiate insulin replacement as needed. FP-1305 must be permanently discontinued for life-threatening (Grade 4) diabetes. Monitoring of blood sugar should be continued to ensure appropriate insulin replacement is utilised.

Adequate evaluation should be performed to confirm aetiology of symptoms related to irAEs. Consultation of endocrinologist is recommended when endocrinopathy is suspected.

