4.1 Dose Limiting Toxicity

DLT evaluable subjects include:

- Part I: All subjects
- Part II: The first three (or six if there is one DLT in the first three) subjects in the following cohorts
 - Q3W cohorts at dose levels that have not previously been tested in Part I
 - Q2W cohorts at each new dose level for the Q2W schema
 - Q1W cohorts at each new dose level for the Q1W schema
- Part III: DLT not applicable

DLT assessment period in Part II is shorter than in Part I, justified by the safety and tolerability data collected during the trial and enabling prompt dose escalation as a part of the 3+3 design of Part II.

- Part I: 63 days (9 weeks) following the first dose of FP-1305
- Part II: 28 days (4 weeks) following the first dose of FP-1305

A DLT is defined as a drug related AE \geq Grade 3 according to NCI-CTCAE version 5.0 occurring during the DLT assessment period and related to FP-1305. The following are exceptions to the rule:

- Grade 3 infusion reactions that resolve within 8 hours from the onset of the reaction are not defined as a DLT
- Grade 3 nausea/vomiting or diarrhea for less than 72 hours with adequate antiemetic and other supportive care are not defined as a DLT
- For thrombocytopenia, haemorrhage is required to qualify grade 3 toxicity as DLT; Grade 4 thrombocytopenia is DLT regardless of haemorrhage
- For neutropenia DLT is as follows,
 - Any neutropenic fever
 - Grade 3 neutropenia persisting $>$ 5 days or Grade 4 neutropenia
- For toxicity judged to be consistent with an acute infusion-related reaction or cytokine release syndrome, DLT will be defined as follows (Sehn 2012):
 - Grade 4 drug-related AE or
 - Grade 3 drug-related AE that cannot be resolved by infusion rate reduction or interruption, or supportive care.
- An AE which, in the opinion of the Investigator, is attributed to a study subject's underlying disease will not be considered a DLT.

In addition, the following are considered DLTs (occurring during the DLT assessment period and related to FP-1305):

- Grade ≥ 2 ALT or AST increase accompanied with bilirubin elevation $>2x$ ULN if baseline value was normal; $>2 \times$ baseline if baseline value was abnormal
- Dose delay of the 2nd cycle due to drug-related toxicity of >14 days

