8.7 Dose Modifications, Infusion Delays, Missed Doses and Special Cases

IMP infusion will be prepared based on the subject's predose weight at each cycle (if not available, the most recent weight should be used). No visit specific dose adjustments are allowed for FP-1305, except for weight change adjustments. However, the maximum amount of FP-1305 in one IMP infusion is 10 g and cannot be exceeded irrespective of the weight-based dose. Guidance will be provided in the Pharmacy Manual to ensure calculated doses do not exceed this limit. If the IMP cannot be administered at the scheduled visit for any reason, the IMP must be administered as soon as possible, below here are instructions for Q3W schema. Instructions for Q2W and Q1W schemas are in Protocol Addendum.

- If the delay is 1 to 7 days, the procedures based on the current visit should be performed, and the subsequent visit will follow 21 days from the date of the infusion that occurred.
- If the delay is more than 7 days, the dose is considered missed, and the next per protocol visit should be brought forward and performed as soon as possible. Note, that the tumour images are still to be taken at every scheduled time point
 - (e.g. if there is an eight day delay for Cycle 4 Day 1, Cycle 4 IMP is considered a missed dose. The infusion given eight days after the original schedule in this case is Cycle 5 IMP dose and the related Cycle 5 procedures should be performed. In addition, tumour imaging of Cycle 4 should be done.) The subsequent visit will follow 21 days from the date of the infusion that just occurred.
 - Cycle 2 is an exception: every effort should be made to ensure that Cycle 2 is not delayed. In unavoidable delay, Cycle 2 IMP administration and the related Cycle 2 procedures should be performed as soon as possible.

Subjects that miss two consecutive scheduled doses (more than 49 days from the previous dose) will discontinue the treatment and enter the follow-up period unless specific consultation and agreement occurs between the investigator, the Medical Monitor and the Sponsor justify continued trial therapy. These decisions must be carefully documented.

Additionally, intra-subject dose change may occur to the recommended Part II/Part III dose after it has been determined. This decision must be carefully documented.

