10.4 Trial Subject Withdrawal/Discontinuation

Administration of the IMP and the subject's participation in the study must be discontinued for any of the following reasons:

- 1) Withdrawal of informed consent
- 2) In the case of any clinical AE, laboratory abnormality or illness leading to the conclusion by the investigator that participation into the trial is not the best interest of the subject
- 3) In the occurrence of toxicities as defined in [Section 8.9](#)
- 4) Pregnancy
- 5) Termination of the trial by the Sponsor
- 6) Loss of ability to freely provide informed consent
- 7) Inability to comply with protocol
- 8) Disease progression (for treatment beyond RECIST defined disease progression see [Section 8.10](#))
- 9) Dosing delays greater than the maximum allowed dosing delays as defined in [Section 8.7](#)

All trial subjects should comply with the protocol specified follow-up procedures as outlined in [Section 8.5](#). The only exception to this requirement is a withdrawal of informed consent for all trial procedures or when a subject has lost the ability to consent freely. All data collected until the withdrawal of informed consent will be analysed and included into trial data.

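### Section 8.9 withholds FP-1305 for a first, related Grade 3 adrenal insufficiency, Section 8.9.2.5 stops it permanently, and the protocol does not say which text governs

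*Protocol*

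**What the plan says.** Protocol Section 8.9 opens with two action lists, both for events at least possibly related to FP-1305.

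- **Withhold list, item 5:** "Grade 2 or 3 endocrinopathy", with a pointer to Section 8.9.2.5.
- **Permanent-discontinuation list, item 7:** "Grade 4 endocrinopathy", with the same pointer.
- **Permanent-discontinuation list, item 10:** "Persistent Grade 2 or 3 adverse reactions (excluding endocrinopathies controlled with hormone replacement therapy and/or immunosuppressants"), when they have not recovered within six weeks and are clinically significant.
- **Permanent-discontinuation list, item 11:** "Any haematological or non-haematological Grade 3 treatment-related adverse reaction that recurs".

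Section 8.9.2.5 then treats the endocrinopathies one by one. Symptomatic Grade 2 adrenal insufficiency leads to withholding. Above that grade, "FP-1305 must be permanently discontinued for severe (Grade 3) or life-threatening (Grade 4) adrenal insufficiency".

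Section 10.4 item 3 makes discontinuation mandatory "In the occurrence of toxicities as defined in" Section 8.9. It does not separate the lists from the subsections.

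**The concern.** One event at one grade gets two different instructions in the same section, and the rule in question is a stopping rule in a first-in-human trial.

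The lists do not say in words that dosing may resume after a Grade 3 endocrinopathy. They imply it in three ways: withholding is set against permanent discontinuation; item 10 spares endocrinopathies controlled on replacement therapy; and item 11 stops dosing for a Grade 3 reaction only when it recurs. A subject with Grade 3 adrenal insufficiency, stabilised on corticosteroid replacement, fits that route. Section 10.2 permits such replacement during treatment.

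A site has some reason to trust the lists. For pneumonitis and nephritis, the permanent-stop grades in 8.9 match those in the subsections.

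At stake is the re-dosing of a subject whom 8.9.2.5 bars from further drug. The event is foreseeable. Section 2.2.1 places CLEVER-1 in the adrenal cortex, and the Part II and III schedules measure cortisol at every cycle. Section 8.8 nevertheless expects immune-related events to be unlikely.

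**Working it through.** The plan gives no figure on this point, so the check is mainly a comparison of texts.

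**Step 1. Action for a first, related event**

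| Event | 8.9 lists | 8.9.2.5 | Agree? |
|---|---|---|---|
| Adrenal insufficiency, Grade 2 | Withhold (item 5) | Withhold if symptomatic | Yes |
| Adrenal insufficiency, Grade 3 | Withhold (item 5) | Permanent stop | **No** |
| Adrenal insufficiency, Grade 4 | Permanent stop (item 7) | Permanent stop | Yes |
| Hypophysitis, Grade 2 or 3 | Withhold (item 5) | Withhold if symptomatic | Yes |
| Hypophysitis, Grade 4 | Permanent stop (item 7) | Permanent stop | Yes |

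Discontinuation item 1 exempts controlled life-threatening endocrinopathies, but item 7 is an independent trigger, so the Grade 4 rows stand.

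**Step 2. Does another discontinuation item catch the Grade 3 event at onset?** Item 1 needs a life-threatening event, item 9 a failed steroid reduction within six weeks, item 10 persistence, and item 11 recurrence. None applies to a first Grade 3 event when it occurs.

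**Step 3. Is precedence stated?** Items 5 and 7 refer to 8.9.2.5 but do not say that it overrides them. Section 10.4 item 3 cites 8.9 as a whole. No precedence rule was found.

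**Step 4. Who could be affected?**

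- A related Grade 3 event inside a DLT window is generally a DLT, and other rules then apply. In Part I, Sections 4.2.2 and 4.2.3 allow continued dosing only for subjects without a DLT. In Part II Q3W escalation, Section 4.3.1 leaves continuation after a DLT to the DMC once the MTD is reached.
- Section 4.1 gives Part III no DLT assessment. In Part II it covers only the first three subjects (six after one DLT) at new exposure levels; for Q3W dosing these are "Q3W cohorts at dose levels that have not previously been tested in Part I".
- In a new-exposure cohort of 10, the number with no DLT window is 10 − 3 = 7, or 10 − 6 = 4 after expansion to six.
- For subjects with a window, the exposure is to events that occur after it closes.

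**Step 5. Ceiling on further dosing.** The Part II and III schedules run to Cycle 17 in the first year. With Q3W infusions on schedule and no dose lost to withholding:

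- No DLT window, event in Cycle 1: 17 − 1 = 16 further infusions, against 0 under 8.9.2.5.
- Part II DLT-evaluable subject, event just after Day 28, which falls in Cycle 2 (Days 22 to 42): 17 − 2 = 15, against 0.

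These are the remaining planned doses, not an estimate of effect.

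**Step 6. How long can dosing wait and still resume?** Section 8.7: "Subjects that miss two consecutive scheduled doses (more than 49 days from the previous dose) will discontinue the treatment", unless continuation is specifically agreed. With a 21-day interval, dosing could resume without such agreement up to 49 − 21 = 28 days after the due date.

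**The case against.** The strongest reply is that the protocol largely resolves this itself. Both list items send the reader to 8.9.2.5. The withhold list says should, while 8.9.2.5 says must. Section 8.9.2.5 is part of 8.9, so 10.4 item 3 reaches it. Permanent discontinuation complies with every text, and harm needs a site to ignore a printed pointer.

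Nor are the lists exhaustive. Some permanent-stop triggers appear only in the subsections, such as recurrent colitis on restarting (8.9.2.2) and steroid-refractory hepatitis (8.9.2.4). Safeguards exist too: Section 11.5 requires any new or worsening autoimmunity to be reported within 24 hours, and 8.9.2.5 recommends an endocrinologist when endocrinopathy is suspected.

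Most of this stands, and it makes the practical risk small. It does not remove the fault. That the specific rule governs is an inference, and Section 13 asks for the protocol to be followed exactly. The list is also more than silent here: item 5 assigns Grade 3 endocrinopathy a different action from the one that 8.9.2.5 requires. The reporting rules could bring the event to the sponsor's attention, but they do not say which instruction applies.

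**Conclusion.** Wrong as written, minor. The conflict is confined to a first, related adrenal insufficiency at Grade 3. A site working from the lists alone could re-dose a subject whom 8.9.2.5 bars. It matters mainly for ongoing or future subjects without a DLT window (Part III, and Part II subjects beyond the first three to six at a new exposure level) and for events after the window. The documents do not give the number of such events. The ceilings of 16 and 15 infusions assume Q3W dosing on schedule for a full first year.

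Three stronger readings are tempting, and the documents do not support them.

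- *The lists authorise re-dosing.* They imply it but never say so, and both texts stop dosing while the event is present.
- *Most Part II subjects were exposed to this conflict.* The Part II SAP (Section 2) says the originally enrolled cohorts have finished treatment. Its Section 9.2 reports 110 subjects in fully enrolled cohorts presented in August 2021, before protocol version 11 of 22 December 2021. The wording of 8.9 in earlier versions is not available, and an edit now could not protect those subjects.
- *The dose-finding or the results are compromised.* DLT status is set by Section 4.1, whichever action follows, so classification, escalation and the analyses are unaffected.

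**What to change.** Keep the stricter, specific rule and bring the two list items into line with it.

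- Withhold item 5: after "Grade 2 or 3 endocrinopathy", add *(except Grade 3 adrenal insufficiency)*.
- Permanent-discontinuation item 7: after "Grade 4 endocrinopathy", add *, or Grade 3 or 4 adrenal insufficiency*.

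Items 1 and 10 need no change, because item 7 triggers discontinuation independently. The cost is a few words in a protocol amendment, with no effect on data collection, sample size or analysis. It is best made before further Part III enrolment, since no Part III subject has a DLT window.
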